## Statistical Analysis Plan

BAY 81-8973 (KOVALTRY) / 19855

Page: 8 of 15

### *Missing or incomplete concomitant medication start and end date or time:*

When computing concomitant medication start dates, if day is missing, it will be imputed as the 15th of the month. If month and day are missing, it will be imputed as 1 July. If necessary, adjust imputed dates so they are not before the birth date.

Other missing data will not be imputed.

### **4.4 Interim Analyses and Data Monitoring**

In case the study will not be completed at the time of next renewal application, the most current results will be delivered for license renewal, and an interim analysis will be performed with all available data.

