## 1. Protocol Summary

### 1.1 Synopsis

**Protocol Title:** A Post-Approval Commitment (PAC) study to evaluate the efficacy, safety, and pharmacokinetics of KOVALTRY in Chinese children, adolescents/adults with severe hemophilia A.

**Short Title:** KOVALTRY Efficacy, Safety, and PK Study in Chinese hemophilia A patients.

**Rationale:** This study is being done to fulfill a post-approval commitment for KOVALTRY received from the China Center for Drug Evaluation (CDE) and China National Medical Products Administration (NMPA).

The marketing authorization of KOVALTRY in China is based on demonstrated safety and efficacy of KOVALTRY in completed studies in previously treated severe hemophilia A patients (PTPs), which included 29 adult Chinese PTPs. China CDE and NMPA requested additional efficacy, safety, and PK data for KOVALTRY in previously treated Chinese hemophilia A patients as well as previously untreated patients (PUPs). The design, objectives, and endpoints for this study were developed in consultation with China CDE. As agreed with CDE, Part A of this planned study will obtain additional efficacy, safety, and pharmacokinetic data for KOVALTRY in Chinese PTPs (children (<12 years of age) and also adult/adolescents ( $\geq 12$  years of age)) with severe hemophilia A. Additionally, as per consultation with CDE, Part B of the study will obtain efficacy and safety data in previously untreated/minimally treated Chinese children (<6 years of age) with severe hemophilia A. The results (at least interim) from this Phase IV study will be submitted with the KOVALTRY licensure renewal application in China.

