**Intervention Groups and Duration:**

The study intervention will be used both for treatment and prevention of bleeding events and with surgical procedures. Individual participant dose decisions are at the discretion of the investigator.

**Part A:** All participants in Part A are expected to be treated for 6 months.

According to the Prescribing Information for KOVALTRY, dose regimens for prophylaxis are:

- Study participants  $\leq$ 12 years: 25 to 50 IU of KOVALTRY per kg body weight (given IV) twice weekly, three times weekly, or every other day according to individual requirements for 6 months
- Study participants  $>$ 12 to 65 years: 20 to 40 IU of KOVALTRY per kg of body weight (given IV) two or three times per week for 6 months

**Part B:** All participants in Part B are expected to be treated for 50 ED. Treatment in Part B may begin with start of prophylaxis with 15 to 50 IU/kg (minimum dose: 250 IU) at least 1 day a week; alternatively, prophylaxis can be started directly with a once-a-week schedule minimum dose of 250 IU for PUPs/MTPs of any weight. The starting dose may be tailored to the participant's weight or demonstrated bleeding tendency.

Study participants who develop high-titer inhibitor ( $>5$  BU/mL, confirmed by local laboratory) related to study drug, that interferes with effective treatment with FVIII, may opt to enter optional ITI treatment with study drug (Section 10.5.1) or leave the study and be treated with other therapies outside of the study at the discretion of the investigator. The optional ITI treatment with the study drug within the study requires a separate signed informed consent. Refer to Section 10.5 for additional details.

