#### 9.4.1 General Considerations

There is no confirmatory comparison planned for this study; study results will be numerically evaluated and compared with the data in the completed LEOPOLD Clinical Trials.

Efficacy analyses outlined in this section only include the data from Part A or Part B (i.e., data from the Optional ITI Treatment are excluded).

For the efficacy endpoints, bleeding events will be presented as summary statistics by age groups.

The annualized bleeding rates for each participant are estimated via

$$\text{Annualized bleeding rate [per year]} = \frac{365.25 \text{ [days per year]} \times (\text{\# of bleeding episodes in treatment period})}{\text{duration of treatment period [in days]}}$$

The treatment period is defined as from the date and time of first study treatment until the date and time of last infusion of study medication, or last visit, whichever is later (not including the Optional ITI Treatment). Before this period is the screening period, after this period is the follow-up period.

Further, for the derivation of analysis variables for bleeding episodes, the following rules will apply:

- “24-hour rule”:  
No more than 1 bleeding episode in a calendar day is counted. If there is more than 1 bleeding episode in a calendar day, to determine which bleeding episodes are counted, priority is given to treated bleeding episodes, spontaneous or trauma bleeding episodes, then joint bleeding episodes. Otherwise, the first bleeding episode in the day is counted. Severity and treatment response will be the worst value of the bleeding episodes of the day. The bleeding site will be aggregated over all bleeding events from that day.
- “72-hour rule”:  
A spontaneous joint or spontaneous muscle bleeding episode will not be counted if it occurs within 72 hours of a prior bleeding episode (or infusion for that bleeding episode) at the same site. For a bleeding episode to be affected by this rule, all sites listed for the bleeding episode must be the same sites specified in the previous bleeding episode. If the current and previous bleeds are both skin/mucosa bleeds, this rule does not apply. Infusions for such bleeding episodes will be considered to be follow-up infusions.

Missing information on date and time of bleeding episodes will be substituted by the date and time of first treatment, if available.

Further handling of missing data will be described in the SAP.

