#### **9.5 Interim Analyses**

In case the study will not be completed at the time of next KOVALTRY license renewal application in China, the most current results will be delivered for license renewal, and an interim analysis will be performed with all available data. This approach has been agreed with CDE.

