#### 4.2 Handling of Dropouts

Annualized number of total bleeds will be calculated for all subjects, including dropouts. Subjects who drop from the study will be included in a listing.

During the study, temporary discontinuation of study drug could happen, the duration of interruption of study intervention (i.e. prophylaxis treatment with KOVALTRY) should not be more than 2 weeks. Prolonged periods ( $> 2$  weeks) or repeated breaks in the prophylaxis schedule should be avoided and could result in the study participant treated as drop out, or being removed from the study.

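### A licence-renewal interim with many participants under about 3 months of treatment can understate the median ABR and overstate the zero-bleed share against the 6-month LEOPOLD Kids figures

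*SAP*

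**What the plan says.** The interim is conditional and tied to a calendar event. SAP 4.4 opens with "In case the study will not be completed at the time of next renewal application" and continues that "the most current results will be delivered for license renewal, and an interim analysis will be performed with all available data"; Protocol 9.5 has the same rule and adds that the approach was agreed with CDE. Protocol 1.1 shows that this may be the analysis the regulator sees: "The results (at least interim) from this Phase IV study will be submitted with the KOVALTRY licensure renewal application in China".

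For Part A, Protocol 1.1 states that "All participants in Part A are expected to be treated for 6 months". Protocol 9.4.1 introduces its formula with "The annualized bleeding rates for each participant are estimated via": 365.25 times the bleeds, divided by the days in that participant's treatment period. SAP 4.5 uses the same formula and ends the period at the later of the last infusion and the last visit. SAP 4.2 keeps short follow-up in: "Annualized number of total bleeds will be calculated for all subjects, including dropouts". SAP 4.1 and 6 then summarise the individual values by mean, SD, median and quartiles, so each participant counts equally. The proportion without bleeds is also a listed endpoint (Protocol 9.4.3, SAP 6.2.2).

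Protocol 9.4.1 says that "study results will be numerically evaluated and compared with the data in the completed LEOPOLD Clinical Trials". SAP 6.2.2 adds, where applicable, a negative binomial regression with treatment duration as offset. It does not say whether that model is produced at the interim.

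**The concern.** A per-participant ABR behaves differently at different lengths of follow-up. After one month a child has either no bleeds, and a rate of 0, or at least one bleed, and a rate of 12 or more. Mixed with 6-month values at equal weight, such results add zeros, which pull on the median and the zero-bleed share, and a few very large values, which widen the spread of the mean.

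The paediatric comparator, LEOPOLD Kids Part A, has 6 months of observation: median 1.90 and mean 3.75 (Protocol 9.2.1), with 45.1% of children free of bleeds (Protocol 12, Clinical Studies). If the renewal analysis mixes short and full follow-up, part of any apparent advantage in the median or zero-bleed share could come from the cut-off date alone. The offset model helps with the mean rate, but not with the median or the zero-bleed share.

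**Working it through.** **Inputs.** 30 children, mean ABR 4, SD 5 (Protocol 9.2.1, SAP 3.1.1); 6 months of treatment. The documents give no accrual plan, so uniform accrual is assumed.

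**The plan's own figure.** 1.96 × 5/√30 = 1.79, interval 2.21 to 5.79. This reproduces the stated 1.8 and 2.2 to 5.8.

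**Model.** Bleeds are Poisson given a child's rate, and rates vary as a gamma distribution. At follow-up f years the variance of an individual ABR is V + 4/f. Setting it to 25 at f = 0.5 gives V = 25 − 8 = 17.

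**Zero-bleed share by follow-up.** P(0 bleeds) = (1 + 17f/4)^(−16/17): 34% at 6 months, 51% at 3 months, 75% at 1 month. Averaged over follow-up uniform on 0 to 6 months it is [4 × (3.125^(1/17) − 1)]/0.5 = 0.555.
- 12-month accrual, cut on its last day: half have 6 months. 0.5 × 0.342 + 0.5 × 0.555 = 45%.
- 18-month accrual, same cut: two thirds have 6 months. 0.667 × 0.342 + 0.333 × 0.555 = 41%.

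**Median by follow-up.** The population median ABR is 2.0 at 6 months, 2.4 at 5 (one bleed, 12/5), 3.0 at 4 (12/4), and 0 at 3 months or less. The effect is therefore not monotone; the downward pull comes from participants below about 3 months.

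**Simulated interims of 30 children (40,000 per row).**

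| Accrual / cut (months) | Expected median | Zero-bleed share | SE of unweighted mean (half-width) | SE of total bleeds / total time (half-width) |
|---|---|---|---|---|
| All at 6 months | 2.45 | 34% | 0.91 (1.8) | 0.91 (1.8) |
| 12 / 12 | about 1.75 | 45% | 1.21 to 1.25 (2.4) | 1.02 (2.0) |
| 18 / 18 | about 2.05 | 41% | 1.13 (2.2) | 0.97 (1.9) |
| 12 / 13 | about 2.2 | 40% | 0.98 (1.9) | 0.97 (1.9) |
| 12 / 14 | about 2.4 | 38% | 0.95 (1.9) | 0.95 (1.9) |

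The mean of both estimators is 4.0 in every row.

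**How firm the half-widths are.** The SE of the unweighted mean is √[(17 + 4·E(1/f))/30], and E(1/f) depends on the shortest follow-up d: over d to 0.5 years it is ln(0.5/d)/(0.5 − d).
- d = 1 day: 10.47. For 12/12, E(1/f) = 0.5 × 2 + 0.5 × 10.47 = 6.24, SE 1.18, half-width 2.3. For 18/18, 4.82, SE 1.10, half-width 2.2.
- d = 7 days: 6.78. The half-widths become 2.1 and 2.0.
- With no lower limit the variance has no finite value, and repeat simulations of 12/12 gave SEs from 1.21 to 1.43.

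So 2.4 and 2.2 are approximate and governed by the few shortest records. The median, the zero-bleed share and the duration-weighted SE were stable.

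**Participants who started at least 6 months before the cut.** About 15 of 30 (12/12) or 20 of 30 (18/18); expected median 2.54 or 2.50, close to 2.45. The half-width of their mean is 1.96 × 5/√15 = 2.5 or 1.96 × 5/√20 = 2.2, no better than with all data. The subset repairs the median and zero-bleed share, not the precision of the mean.

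**Part B.** One in-window bleed in 28 days is 365.25/28 = 13.0 per year. In a 6-child mean this is a shift of (13.0 − 1.9)/6 = 1.9, as large as the mean of 1.9 assumed in Protocol 9.2.2.

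**The case against.** The strongest reply is that nothing in the documents shows that any Part A participant would be short of 6 months. The interim runs only if the study is incomplete, accrual is not described, and the larger figures place the cut on the last day of accrual. That stands: these are conditional sizes, and two months' delay nearly removes the effect on the median. A reader might infer that any participant short of 6 months lowers the median. The model does not support that: with 5 of 30 children at 3 months the expected median is 2.45 against 2.44, and 4 to 5 months can raise it. A single interim's median also has a sampling SD of about 1.2 at the 12/12 cut, more than the shift of 0.7. The shift is nonetheless systematic, and always in the favourable direction when many are very short.

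Second, the mean is unbiased, and the ±1.8 was set for the planned analysis, not as an interim standard. Both are correct, and the duration-weighted rate does not reach 1.8 at those cuts either.

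Third, SAP 6.2.2 already contains the offset model, the study tests no hypothesis (Protocol 9.1), and CDE agreed to an interim on available data. This narrows the point but does not close it. The model is conditional, is not tied to the interim, and leaves the median and zero-bleed share untouched. The agreement recorded in Protocol 9.5 does not mention how unequal follow-up is summarised.

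**Conclusion.** The point holds in conditional form. If a substantial share of Part A has less than about 3 months of treatment at the cut, the unweighted summaries can lower the expected median by about 0.4 to 0.7 bleeds per year and raise the zero-bleed share by 7 to 11 percentage points, with efficacy unchanged. They also widen the interval of the mean from 1.8 to roughly 2.2 to 2.4. This rests on uniform accrual cut at its end, follow-up length unrelated to bleeding, and a negative binomial fitted to the plan's mean and SD. That model gives 34% zero-bleeders at 6 months against the 45.1% reported in LEOPOLD Kids, so in practice the median could reach 0 more easily than simulated.

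Two stronger readings are not supported. One is that the interim mean ABR is biased: it is 4.0 in every scenario tried. The other is that the 6-month comparison covers all of Part A: the adolescent/adult LEOPOLD figures are one-year (Protocol 12, Tables 8 and 9), so the argument applies to children only.

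**What to change.** Add to SAP 4.4 and 6.2, and mirror in Protocol 9.5:

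1. At any analysis with incomplete follow-up, always report for Part A the negative binomial rate with duration offset already in SAP 6.2.2, with its 95% CI, beside the unweighted mean. For Part B (about 6 children), report the crude rate, 365.25 × total bleeds / total days, and the model only if it converges. Do not describe the two as the same estimator: with unequal follow-up they differ, by about 0.14 bleeds per year on average for 30 children at the 12/12 cut.
2. For Part A, also give the median, quartiles and zero-bleed share for participants who started treatment at least 6 months before the cut-off, dropouts included. List the others with their bleeds and days.
3. For Part B, list each child's bleeds and days, and do not restrict summaries to those who have reached 50 ED. Protocol 7.2 says that the time to 50 ED depends on the number of bleeds, so that subset could over-represent frequent bleeders.
4. State the data cut-off and how the treatment period ends for ongoing participants.

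The cost is SAP wording and one extra table, with no new data and no change to conduct. The small downside is that the Part A subset summaries rest on fewer participants, about 15 to 20 of 30 in the examples.

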### **4.5 Data Rules**

All bleed and infusion data will be entered into the electronic patient diary (hospital infusions will be entered into an eCRF) and imported into SAS. If an infusion is given for a bleed and the bleed information is not provided, the infusion date will be used as the bleed date. Bleeds occurring before start of prophylaxis treatment with study medication will not be counted.

Bleeding rate will be annualized using the following formula:

Annualized bleeding rate [per year] =

365.25 [days per year] x (# of bleeding episodes in treatment period) / duration of treatment period [in days]

The treatment period (exclude optional ITI period) is defined as from the date and time of first study treatment, until the date and time of last infusion of study medication, or last visit, whichever is later.

- “24-hour rule”: No more than 1 bleeding episode in a calendar day is counted. If there is more than 1 bleeding episode in a calendar day, to determine which bleeding episodes are counted, priority is given to treated bleeding episodes, spontaneous or trauma bleeding episodes, then joint bleeding episodes. Otherwise, the first bleeding episode in the day is counted. Severity and treatment response will be the worst value of the bleeding episodes of the day. The bleeding site will be aggregated over all bleeding events from that day. Regardless of which bleed is selected, the time of the first bleed in the day will be used. All other infusions in the day for treating bleeds will be considered follow-up infusions.
- “72-hour rule”: A spontaneous joint or spontaneous muscle bleeding episode will not be counted if it occurs within 72 hours of a prior bleeding episode (or infusion for that bleeding episode) at the same site. For a bleeding episode to be affected by this rule, all sites listed for the bleeding episode must be the same sites specified in the previous bleeding episode. If the current and previous bleeds are both skin/mucosa bleeds, this rule does not apply. Infusions for such bleeding episodes will be considered to be follow-up infusions.

See example below how these bleeds will be counted.

- Subject 1 reported => in analysis data set

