### 3.2 Objectives and Endpoints - Part B (PUPs/MTPs)

Objectives	Endpoints
Primary Efficacy	

 
Assess the efficacy of KOVALTRY within 48 hours of previous prophylaxis infusion in previously untreated/minimally treated Chinese children (<6 years of age) with severe hemophilia A
 
	
 
ABR within 48 hours of previous prophylaxis infusion
 

Secondary Efficacy	

 
Evaluate the efficacy of prophylaxis treatment with KOVALTRY
 
Assess the efficacy of KOVALTRY for treatment of bleeding episodes
 
Evaluate the in vivo recovery of KOVALTRY
 
Hemostatic control for minor surgeries
 
	
 
ABR during the prophylaxis period
 
Number of infusions required to treat a bleed and response to treatment of bleeds
 
In vivo recovery of KOVALTRY at baseline and study end
 
Physician assessment of adequacy of hemostasis in minor surgery
 

Safety	

 
Assess the safety of KOVALTRY for prophylaxis and treatment of bleeding episodes in previously untreated/minimally treated Chinese children (<6 years of age) with severe hemophilia A
 
	
 
FVIII inhibitor development by the Nijmegen Bethesda assay
 
Treatment-emergent adverse events (TEAEs)
 

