#### 4.1.2 Part B (PUPs/MTPs)

Part B will assess the efficacy and safety of KOVALTRY in previously untreated/minimally treated Chinese children with severe hemophilia A. Part B will investigate approximately 6 PUPs/MTPs. Efficacy and safety assessments are outlined in the SoA in Section 1.3.2.

Efficacy and safety data for the use of KOVALTRY for treatment of bleeding episodes will also be collected.

- Study participants will be treated until at least 50 ED is achieved.
  - Treatment may begin with start of prophylaxis with 15 to 50 IU/kg (minimum dose: 250 IU) at least 1 day a week; alternatively, prophylaxis

can be started directly with a once-a-week schedule minimum dose of 250 IU for PUPs/MTPs of any weight.

- The starting dose may be tailored to the participant's weight or demonstrated bleeding tendency.
- Individual participant dose decisions are at the discretion of the investigator.
- Part B will include 8 study visits (Screening, Baseline, Visit 3 [approximately 5 ED], Visit 4 [approximately 10 ED], Visit 5 [approximately 15 ED], Visit 6 [approximately 20 ED], Visit 7/Interim visit [approximately 30 to 40 ED], and Visit 8/Final visit [50 ED]/Early Termination). All parents/caregivers of participants in Part B will receive a safety follow-up call approximately 2 weeks after the end of treatment.

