**Type of Participant and Disease Characteristics**

2. Chinese participants with severe hemophilia A (defined as FVIII:C <1% with one-stage clotting assay documented at the time of screening). If screening results show FVIII:C as equal to or higher than 1%, then severe hemophilia A may be confirmed by documented historical evidence from a (certified) clinical laboratory demonstrating FVIII:C <1% as determined by a one-stage clotting assay.
3. PUPs must have no previous exposure to any FVIII product.  
MTPs must have no more than 1 ED with any purified FVIII concentrate or 3 exposures with FFP or cryoprecipitate.
4. MTPs have no current evidence of inhibitor antibody as measured by the Nijmegen-modified Bethesda assay (<0.6 BU/mL) in 2 consecutive samples and must have absence of clinical signs or symptoms of decreased response to FVIII administration. Testing for the 2 negative samples must be performed by the local laboratory at least 1 week but not more than 2 weeks apart. Participants may not receive FVIII product within 72 hours prior to the collection of samples for inhibitor testing.

5. PUPs and MTPs must observe a 6-month washout period if they have received subcutaneous factor substitution therapy (emicizumab).
6. PUPs may be included if they will receive their first FVIII dose with KOVALTRY for treatment of first bleeds and agree to start prophylaxis as part of their care.  
MTPs may be included if they agree to start prophylaxis as part of their care.

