### 6.6.2 Dose Modification in Part B (PUPs/MTPs)

Individual participant dose decisions are at the discretion of the investigator.

Recent studies have demonstrated that the timing of the first exposures to FVIII may be critical for the tolerance of the drug. The CANAL study showed that early intensive treatment, such as those required for surgery or severe bleeds, increased the risk for inhibitor development, whereas regular prophylaxis was associated with a lower risk. This observation was subsequently supported by studies demonstrating lower inhibitor rates in boys treated with low dose early prophylaxis in treatment centers in Germany.

Taking these observations into account, the following are treatment recommendations for PUPs/MTPs participating in Part B:

1. Prophylaxis can be started directly with 15 to 50 IU/kg (minimum dose: 250 IU) once per week; the starting dose may be tailored to the participant's weight or demonstrated bleeding tendency.
2. Alternatively, treatment can be initiated with an on-demand regimen. Prophylaxis should begin after a minimal number of on-demand FVIII exposures with KOVALTRY (no more than 2 to 3 bleeding events) or when the child is large enough to tolerate weekly infusion.
3. Avoid starting prophylaxis during a febrile illness or other identified inflammatory events.
4. Avoid surgery or need for high dose intensive treatment lasting more than 4 days during the first 20 ED.

5. KOVALTRY must not be given as prophylaxis for vaccinations.

After treatment with KOVALTRY begins, inhibitor testing every 3 to 5 ED is required until 20 ED are accumulated or in case of non-response to treatment.

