### 7.2.2 Visit 2/Baseline (No Later Than 4 Weeks From Visit 1)

For MTPs, this visit will include the first administration of study drug.

For PUPs, the first dose of KOVALTRY may be for treatment of a bleed. First treatment should not occur during high risk situations, surgery, or bleeds requiring prolonged or intensive treatment (see Section 6.6.2).

The following activities will be performed:

- Inclusion/exclusion criteria verification, i.e., confirmation of eligibility including check of laboratory test results.  
Note: MTPs must be inhibitor negative as evaluated via local laboratory testing at the Screening visit. A confirmatory inhibitor test must be taken at least 1 week but not more than 2 weeks after the Screening visit. Results from local laboratory testing must be negative ( $<0.6$  BU/mL) prior to administration of study intervention.
- Height/length and weight
- Vital signs (including systolic and diastolic blood pressure, heart rate, and body temperature); blood pressure may be deferred if the appropriate cuff size or equipment is not available (see Section 8.2 for details)
- Concomitant medication review
- Blood sampling before administration of study drug intervention
  - FVIII inhibitor assessment (Section 8.10; not required for PUPs but required for MTPs)

- In-hospital administration of the first dose of study drug (for MTPs and PUPs who are starting treatment at baseline).  
Note: First exposure to study drug may be either for treatment of an uncomplicated bleed or for start of prophylaxis. Inhibitor testing is mandatory every 3 to 5 ED until 20 ED are accumulated (see Section 6.6.2).
- Blood sampling after administration of study intervention (Section 7.3.2):
  - Incremental recovery (15 to 30 minutes post infusion) only for participants who start prophylaxis at Baseline; for PUPs who do not start prophylaxis at baseline, recovery should be done when prophylaxis is started
  - AE review
  - Study drug dispensation for home infusions in accordance with the IxRS drug dispensing schedule
  - Diary training review; participants/caregivers will be instructed to complete the EPD as required (see Section 7.3.1) beginning at Baseline through the end of the study (see Section 4.4)
  - Instruction on the prophylaxis regimen to be administered to the participant
  - Begin regular biweekly contact between the participant's parent/caregiver and the site to check EPD documentation and AE review until the End of Study/Early Termination

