#### 6.2.2 Secondary Endpoint(s)

Spontaneous bleeding episodes, trauma bleeding episodes, joint bleeding episodes, and other bleeding episodes types will be summarized separately.

Other efficacy variables are:

- ABR of treated bleeding episodes (total, joint, spontaneous, trauma)
- ABR of target joint bleeding episodes
- ABR of bleeding episodes within 48h of previous prophylaxis infusion (total, joint, spontaneous, trauma) [for Part A]
- ABR of total bleeding episodes during prophylaxis treatment [for Part B]
- Study participant's/caregiver's assessment of response to treatment of bleeding episodes (excellent, moderate, good, or poor)
- Physician's assessment of the response to treatment of bleeding episodes in minor surgery (excellent, moderate, good, or poor)
- Evaluate proportion of patients without bleeding episodes
- The number of infusions per bleeding episode
- Factor VIII usage (expressed as number of infusions and IU/kg per year, as well as
- IU/kg per event)
- Incremental recovery

For subjects undergoing surgery (both major and minor), number of surgery infusions, and total doses will be summarized and listed for these subjects.

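### SAP 4.5 excludes bleeds before prophylaxis without naming an endpoint; read as written, it takes KOVALTRY-treated on-demand bleeds out of the Part B treatment-of-bleeds summaries

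*SAP*

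**What the plan says.** SAP 4.5 (Data Rules): "Bleeds occurring before start of prophylaxis treatment with study medication will not be counted". The next item in the section is the ABR formula. The 24-hour and 72-hour rules follow, and then a rule for assigning infusions to bleeds.

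The protocol foresees bleeds of this kind in Part B:

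- Section 6.6.2, after describing a direct start of prophylaxis: "Alternatively, treatment can be initiated with an on-demand regimen". Prophylaxis is then to begin after at most two or three bleeding events.
- Section 5.1.2, criterion 6: "PUPs may be included if they will receive their first FVIII dose with KOVALTRY for treatment of first bleeds".
- Section 7.2.2: "First exposure to study drug may be either for treatment of an uncomplicated bleed or for start of prophylaxis".

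The endpoint concerned is a Part B secondary efficacy endpoint in protocol 3.2: "Number of infusions required to treat a bleed and response to treatment of bleeds". It carries no period limit. Neither does its SAP counterpart in 6.2.2, "The number of infusions per bleeding episode". Protocol 4.1.2 adds: "Efficacy and safety data for the use of KOVALTRY for treatment of bleeding episodes will also be collected".

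Protocol 9.4.1 gives the same ABR formula and the same two counting rules as the SAP but has no exclusion of bleeds before prophylaxis. Its treatment period begins at the first study treatment.

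**The concern.** Leaving out bleeds that precede prophylaxis makes sense for a bleeding rate that is meant to describe prophylaxis. It does not suit an endpoint that asks how well KOVALTRY treats a bleed. A bleed treated on demand with study drug, with its infusions and response recorded in the diary, is direct evidence for that endpoint whether or not prophylaxis has begun.

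Part B has about 6 children and few bleeds in total. The bleeds at issue would not be a random subset: they are each child's first exposures, and they occur without prophylactic cover. If they are dropped, the reported response and infusions per bleed describe bleeds on prophylaxis only, and the tables need not tell the reader so.

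**Working it through.** The plan gives no figure for the number of on-demand bleeds, so there is nothing of its own to reproduce on this point. The check has two parts.

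**1. What the rule reaches as written**

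- *Response to treatment.* The 24-hour rule in SAP 4.5 assigns the worst response of the day to the counted bleed. The section is therefore not confined to ABR.
- *Infusions per bleed.* SAP 4.5 also sets how infusion records are sorted to count infusions for each bleed.
- *Meaning of counted.* The 72-hour rule uses the same expression. Its example shows the effect in the analysis data set: an uncounted bleed stops being a bleed record and becomes a follow-up infusion. A programmer could reasonably treat a bleed before prophylaxis as absent from all bleed summaries.
- *Main Part B ABRs.* The primary ABR requires a previous prophylaxis infusion within 48 hours, and the secondary ABR is defined during prophylaxis (SAP 6.2.1 and 6.2.2). Both numerators leave out these bleeds by definition, so the rule changes neither.
- *Restoration elsewhere.* No section of the protocol or SAP puts these bleeds back into the treatment-of-bleeds summaries.

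**2. How many bleeds could be involved**

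Inputs:

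| Input | Value | Source |
|---|---|---|
| Children in Part B | 6 | Protocol 9.2.2 |
| Time on prophylaxis, T | 0.5 to 1 year | Protocol 7.2.8 (6 to 12 months for most) |
| Bleeds per year on prophylaxis | 4 | Assumption: Part A planning value, protocol 9.2.1; no total ABR is given for Part B |
| Lead-in bleeds per on-demand starter, b | 1 to 3 | Assumption within the protocol 6.6.2 limit |
| Children starting on demand, k | 0, 3 or 6 | Assumption; not given |

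Bleeds kept = 6 × 4 × T = 12 (half a year) to 24 (one year).

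Share dropped = k·b / (k·b + bleeds kept).

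| k | Smallest share | Largest share |
|---|---|---|
| 0 | 0% | 0% |
| 3 | 3/(3 + 24) = 11% | 9/(9 + 12) = 43% |
| 6 | 6/(6 + 24) = 20% | 18/(18 + 12) = 60% |

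*Sensitivity.* Take 2 to 3 lead-in bleeds per starter and 1.9 to 3.75 bleeds per year on prophylaxis. The lower rate is the 48-hour ABR in protocol 9.2.2, which omits later bleeds. The upper is the total ABR in treated children in 9.2.1. Bleeds kept are then 6 × 1.9 × 0.5 = 5.7 to 6 × 3.75 × 1 = 22.5.

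- k = 3: 6/(6 + 22.5) = 21% to 9/(9 + 5.7) = 61%.
- k = 6: 12/(12 + 22.5) = 35% to 18/(18 + 5.7) = 76%.

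The ranges depend on the assumed rate and above all on k. The base is all bleeds on prophylaxis, whereas the endpoint concerns treated bleeds.

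**The case against.** The best reply is that the sentence was meant for ABR only. It stands directly before the annualization formula, and its verb is the one used for bleed counts in the rules that follow. That reading is not empty. The ABRs of treated, joint, target joint, spontaneous and trauma bleeds in protocol 7.3 and SAP 6.2.2 are not expressly limited to prophylaxis, so the exclusion would do real work there.

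SAP section 1 also places full table and dataset specifications in separate documents that form part of the plan. They were not supplied and may settle the scope. Protocol 6.6.3 ties the response scale to breakthrough bleeds, which gives some support to a prophylaxis-only endpoint. Against that, protocol 7.3.1 requires a response for any bleed treated with KOVALTRY.

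The consequences are bounded as well. The study is descriptive. SAP section 6 has all data listed, so the bleeds would leave the summary tables but not the report. Prophylaxis from the outset is the leading description of Part B dosing in protocol 4.1.2, so few or no children may start on demand.

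What stands: the intention may have been narrow, and the loss may be zero. What does not: nothing in the supplied text limits the sentence, and its section governs the very variables that make up the treatment-of-bleeds endpoint.

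**Conclusion.** The point holds as a defect of scope. Applied as written, SAP 4.5 removes from the Part B summaries of response, infusions per bleed and IU/kg per event those KOVALTRY-treated bleeds that the protocol allows before prophylaxis and that fall within a stated secondary endpoint. The size runs from 0% upward: 11% to 43% of bleeds with 3 on-demand starters and 20% to 60% with 6, on the assumptions of 4 bleeds per year, 0.5 to 1 year of prophylaxis and 1 to 3 lead-in bleeds.

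A reader might infer three stronger things that the documents do not support:

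- *That the bleeds are certain to be lost.* The intended scope is not stated, and the detailed specifications were not seen.
- *That the headline Part B bleeding rates change through this exclusion.* Their numerators do not.
- *That the result would be biased in a known direction.* No data show whether response to on-demand bleeds is better or worse than response to bleeds on prophylaxis.

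The change should be made, but no primary result depends on it.

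**What to change.** Limit the SAP 4.5 sentence to the ABR endpoints. Then state that response to treatment, infusions per bleed and IU/kg per event include every bleed treated with KOVALTRY from the first study dose, excluding the optional ITI period, with results shown separately before and after the start of prophylaxis. Align the table and dataset specifications with this.

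The cost is one SAP sentence and one table column. The data are already collected in the diary and CRF, and no dosing rule, visit or sample size changes. If only the ABRs were meant from the start, the same sentence simply records that.
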